3. PRIMARY AND SECONDARY VARIABLES

3.1 General definitions

Baseline for FEV₁ will be defined as the mean of the 2 measured values for the corresponding variable (2 measurements 45 min apart, at -1 hour and -15 min), prior to the morning IP administration on Day 1 of each treatment period. If both are missing, the Visit 2 pre-bronchodilator value will be used instead. If one of the values is missing, the available value will be used as baseline.

All baseline values for efficacy analysis will be the pre-dose values of each treatment period except for the Total BCSS questionnaire score, where the last 14 days of the run-in period baseline will be used for all treatments in each sequence.

The baseline for daily rescue medication use will be the daily average of puffs recorded in the e-Diary during the last 14 days of the run-in period; this baseline will be used as baseline for all treatment periods.

For vital signs, laboratory variables (including i-STAT) and 12-lead ECG variables, baseline is defined as the values obtained prior to the morning IP administration on Day 1 of Visit 3.

The cough VAS measurement done at pre-dose on Day 1 of each treatment period will be used as a baseline. For cough monitoring, the assessment done starting 24 hours prior to dosing on Day 1 will be regarded as a baseline of each treatment period.

For COPD assessments (CAT), baseline is defined as the value obtained at Screening (Visit 1 or Visit 2).

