7. DISCONTINUATION OF TREATMENT AND SUBJECT WITHDRAWAL

7.1 Discontinuation of study treatment

Patients may be discontinued from IP in the following situations.

- Patient decision. The patient is at any time free to discontinue treatment, without prejudice to further treatment.
- Adverse Event.
- Severe non-compliance with the Clinical Study Protocol.
- Failure to meet randomisation criteria: Violations of inclusion and/or exclusion criteria detected after randomisation. See Section 7.3 for patients not fulfilling inclusion/exclusion criteria but detected after randomisation.
- Lost to follow-up: See Section 7.2 for details.
- Pregnancy: In case of pregnancy the female patient will be immediately discontinued from study treatment.

- Clinical/FEV₁ stability criteria not fulfilled during the treatment periods.
- Development of study-specific withdrawal criteria: These criteria are listed below; in the event that any of these conditions are reported as an AE, then this AE should be reported as the primary reason for discontinuation in the eCRF.
- Withdrawal of consent to the use of donated biological samples.

(a) Vital signs (any time after randomisation; the test must be repeated to confirm that withdrawal criterion has been met)

- Systolic blood pressure (SBP) increase of >40 mmHg from pre-dose at Day 1 of each treatment period AND SBP >180 mmHg at any time within the 12-hour interval after taking study treatment.

(b) Laboratory findings (any time after randomisation; the test must be repeated to confirm that withdrawal criterion has been met)

- Haematologic toxicity defined as 1 or more of:
 - Confirmed leucocyte count $<2.0 \times 10^9/L$.
 - Confirmed neutrophil count $<1.0 \times 10^9/L$.
 - Confirmed platelet count $<75 \times 10^9/L$.
 - Confirmed lymphocyte count $<0.5 \times 10^9/L$.
- Hepatic toxicity defined as 1 or more of:
 - Confirmed alanine aminotransferase (ALT) or aspartate aminotransferase (AST) increase to $>3 \times$ the upper limit of normal (ULN).
 - Confirmed isolated total bilirubin (TBL) increase to $>2 \times$ ULN.
 - Confirmed ALT or AST increase to $>2 \times$ ULN concurrent with an increase in TBL to $>1.5 \times$ ULN.
- Serum potassium, checked within 4 hours post-dose on the days tested, <3.0 mmol/L, will be treated appropriately by the Investigator, and the patient will be withdrawn from study treatment.

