(c) ECG (within 4 hours of post-IP dosing; the test must be repeated to confirm that withdrawal criterion has been met):

- Symptomatic bradycardia defined as heart rate <45 bpm or asymptomatic bradycardia defined as resting supine pulse <30 bpm while awake, persisting for at least 10 min.

- Heart rate of >120 bpm and an increase of >40 bpm during the first 4 hours post-dose, persisting for at least 10 min.
- QTcF interval prolongation exceeding >500 ms during the treatment period OR >60 ms change from pre-dose at Day 1 of each treatment period (within 4 hours post-dose), persisting for at least 5 min.

(d) Lung function

- FEV₁ decrease by >20% from pre-dose at Day 1 of each treatment period (ie, before first dose of study treatment) on 2 consecutive spirometry assessments obtained at least 15 min apart AND with associated symptoms of dyspnoea at any time within the first 2-hour interval after taking study treatment.

(e) Moderate to severe COPD exacerbation

- COPD exacerbation of moderate or severe intensity.

Note: A COPD exacerbation is defined as a change in the patient's baseline dyspnoea, cough, and/or sputum (increase in volume or change in colour towards purulence) that lasts ≥ 3 days, is beyond normal day-to-day variations, is acute in onset, and may warrant a change in regular medication. The severity of COPD exacerbations is classified as follows:

- Mild: Exacerbations that do not require systemic steroids or antibiotics and do not result in hospitalisation or death.
- Moderate: Exacerbations that require treatment with systemic steroids and/or antibiotics, and do not result in hospitalisation or death.
- Severe: Exacerbations that result in hospitalisation or death.

(f) Other

- Study cancellation or any other reason not described above.
- Patient withdrawal due to death.

Generally, before discontinuation of a patient from the study, a discussion between Sponsor's Study Physician and Investigator is encouraged, as much as feasible.

See the SoA ([Table 1](#)) for data to be collected at the time of treatment discontinuation and follow-up and for any further evaluations that need to be completed.

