3.1.2 Repeated and unscheduled visits

All repeated and unscheduled measurements will be presented in the listings. Repeated and unscheduled measurements will not be used for statistical analysis or summary tables, unless the repeated measurement was performed due to unreliable values/technical reasons, or the repeated measurement occurred prior to IP administration and is defined as the 'baseline'. The following general rules will apply to all repeated and unscheduled measurements (the below section describes a different approach for spirometry variables):

- For repeated measurements obtained prior to the first dose of IP in each period, the latest reliable value (which may be scheduled or unscheduled) will be used in the calculation of descriptive statistics
- For repeated measurements obtained at the designated Baseline visit, the latest reliable value (which may be scheduled or unscheduled) will be defined as the Baseline in each period. Repeated measurements designated Baseline will be used in descriptive statistics rather than the planned measurement they replace
- For repeated measurements obtained at any time point after the first dose of IP, the first reliable value of any repeated measurements will be used in the calculation of changes from Baseline and for the descriptive statistics.

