4.4.1.3 ECG

All ECG data collected will be listed.

Mean absolute values and mean change from baseline for continuous ECG parameters will be summarised by treatment, day (Day 1, 8, and 14) and timepoint within day, 95% CIs for the change from baseline will be provided in addition to the usual descriptive statistics parameters.

Graphical presentation of mean change from baseline (and SE) for ECG parameters by treatment and timepoint will also be provided.

For HR, and QTcF parameters, change from baseline at each timepoint within Day 1, Day 8, and Day 14 will be analysed by means of a mixed model; a random effect model with fixed effects for treatment, sequence, and period. The patient will be fitted as a random effect and the pre-dose value of the parameter obtained at visit 3 will be included as a covariate. Between-groups difference in LSM means will be provided with their 90% CI. A Figure presenting the LSM means and 90% CI across time will be presented as well.

QTcF exceeding ICH boundaries are defined in Table 4. Other ECG values (HR, QRS interval, and PR interval) are defined to be PCS if they meet criterion 1 or criterion 2 displayed in Table 5. Number and percentages of patients with post-baseline QTcF exceeding ICH boundaries and PCS ECG values will be presented for each category, each criterion defined in Table 4 and Table 5.

These numbers and percentages of patients with post-baseline QTcF exceeding ICH boundaries and PCS ECG values will be summarised by treatment overall and by timepoint within each day (Day 1, 8, and 14).

A listing of individual data for all patients with PCS ECG values will be provided, and will include treatment sequence, patient number, and all ECG values (baseline and post-baseline values), clinical relevance of PCS assessed by the PI will also be in the listing.

A listing of all treatment-emergent AEs recorded for patients with PCS ECG values (at baseline or post-baseline) will also be provided.

The number and percentage of patients with post-baseline abnormal ECG findings (Rhythm, Extra Systoles, Conduction, ST-Changes, ST Segment, T Wave Observations, and U Wave Observations) will be summarised by treatment, overall and by timepoint within each day (Day 1, 8, and 14).

Percentages will be based on the number of patients with at least one post-baseline ECG assessment.

A listing of all ECG abnormal findings will be provided.

Table 4 PCS ECG criteria: QTcF exceeding ICH boundaries

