
Category 1: QTcF value above the following cut-off at any time during treatment
 
Criteria:
 
 >450 (ms) >480 (ms) >500 (ms) 
Category 2: QTcF increase by more than following cut-off at any time during treatment
 
Criteria:
 
 >30 (ms) >60 (ms) >90 (ms) 
Category 3: QTcF value above cut-off and QTcF increase by more than cut-off at any time during treatment
 
Criteria:
 
 Value >450(ms) and Increase >30(ms) Value >500(ms) and Increase >60(ms)
--

Table 5 PCS ECG criteria: Heart Rate and QRS interval

ECG parameter	Category	Criterion 1	Criterion 2
Heart rate	Tachycardia event	≥ 110 bpm and an increase of $\geq 15\%$ over baseline value	≥ 120 bpm if baseline is < 100 bpm
	Bradycardia event	≤ 50 bpm and a decrease of $\geq 15\%$ over baseline value	≤ 40 bpm if baseline is > 40 bpm
QRS interval		≥ 100 msec and an increase of $\geq 25\%$ over baseline value	≥ 150 msec if baseline is < 150 msec
PR interval		≥ 200 msec and an increase of $\geq 25\%$ over baseline value	≥ 250 msec if baseline is < 250 msec

bpm = beats per minute.

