5. INTERIM ANALYSES (NOT APPLICABLE)

6. CHANGES OF ANALYSIS FROM PROTOCOL

Change in the analysis set used:

All demographic and baseline characteristics will be analysed using the full analysis set instead of the safety population.

Change in definition of baseline for vital signs, laboratory variables including i-STAT glucose and potassium and ECG variables:

Baseline is defined as the last assessment made before the first dose of IP in each period instead of the value obtained prior to the morning IP administration on day 1 of Visit 3

For HR, and QTcF parameters:

Analyses of change from baseline at each day and timepoint within day will be performed instead of the analysis of AUC₀₋₄ at Day 1, Day 8, and Day 14 and AUC₀₋₂₄ at Day 1 and Day 14. No formal analysis of other ECG parameters will be performed.

Dropouts due to lack-of-efficacy during treatment periods added as a COPDCompEx event.

Additional analysis on FEV1:

Statistical analyses on the change from baseline in FEV1 15 min, 30 min, 1, 2, 4, 8, 23, and 23:45 hours post-dose will be presented by treatment group at Day 1 and Day 15.

Also, analyses on the change from baseline in FEV1 15 min, 30 min, 1, 2, and 4 hours post-dose will be presented by treatment group at Day 8.

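### The SAP gives two conflicting baselines for vital signs, laboratory and ECG data, and the heart rate/QTcF model keeps the Visit 3 covariate that SAP Section 6 has abandoned

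*SAP*

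**What the plan says.** SAP 3.1 (General definitions) covers vital signs, laboratory variables including i-STAT, and 12-lead ECG variables. It states that "baseline is defined as the values obtained prior to the morning IP administration on Day 1 of Visit 3". Protocol 9.4.2 says the same.

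SAP Section 6 (Changes of analysis from protocol) names the same variables and says the definition was changed: "Baseline is defined as the last assessment made before the first dose of IP in each period instead of the value obtained" before dosing at Visit 3. SAP 3.1.2, on repeated measurements, also assumes a period baseline: "the latest reliable value (which may be scheduled or unscheduled) will be defined as the Baseline in each period".

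SAP 4.4.1.3 analyses change from baseline in heart rate and QTcF at each time point. It has fixed effects for treatment, sequence and period, and a random patient effect. The covariate is explicit: "the pre-dose value of the parameter obtained at visit 3 will be included as a covariate". The section does not say which baseline the change is taken from. Table 4 in that section counts patients with a "QTcF increase by more than following cut-off at any time during treatment", again without naming the reference value.

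**The concern.** A programmer who follows 3.1 and one who follows Section 6 would produce different safety tables from the same data. Section 6 is a current statement of the planned analysis, not a log of superseded text, so the conflict cannot be set aside.

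The choice affects:

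- QTcF Categories 2 and 3 in Table 4
- the potentially clinically significant (PCS) flags for heart rate, QRS, PR and blood pressure in Tables 5 and 6
- the laboratory shift, New and Worsened classes
- the heart rate and QTcF treatment differences with their 90% confidence intervals

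Absolute QTcF cut-offs, the laboratory Notable limits and the FEV1 analyses do not depend on it.

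Heart rate deserves care here. Protocol 2.3 reports it as the only safety outcome with a dose response in an earlier multiple-dose study and asks for further exploration. Left unresolved, the safety baseline could be chosen after unblinding.

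**Working it through.** **Text.** The two readings side by side:

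| If this governs | Response in 4.4.1.3 | Covariate in 4.4.1.3 | Consequence |
|---|---|---|---|
| SAP 3.1 | change from Visit 3 | Visit 3 value | model coherent, Section 6 false |
| SAP Section 6 | change from period pre-dose | Visit 3 value | response and covariate use different baselines |

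The FEV1 models in SAP 4.2.2 pair like with like: period baseline with period covariate, and first-period baseline with first-period covariate in the sensitivity analysis.

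**Extent.** Planned patient-periods: 72 × 3 = 216. In Period 1 the two baselines normally coincide, so 72 × 2 = 144 are affected. Day 1 to Day 14 is 13 days and wash-out is 42 to 49 days from the last dose. Visit 3 therefore precedes Period 3 dosing by 2 × (13 + 42) = 110 to 2 × (13 + 49) = 124 days.

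**False QTcF increases above 30 ms.** The plan states no figure to reproduce and no QTcF variance. Assumptions: within-period SD 8 ms, between-period SD s = 2, 5 or 10 ms, no drug effect.

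- Period baseline, one reading: SD of change = √(2 × 64) = 11.3; P(>30) = 0.40%.
- Visit 3 baseline in Periods 2 and 3: SD = √(2(64 + s²)) = 11.7, 13.3, 18.1; P = 0.50%, 1.23%, 4.88%.
- Pooled over three periods, (0.40 + 2P)/3 = 0.47%, 0.95%, 3.4%.

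At any time, over 11 post-baseline readings (Day 1: 1, 2, 4, 24 h; Day 8: 1, 4 h; Day 14: pre-dose, 1, 2, 4, 24 h): P = 1 − E[Φ((30 + U)/8)¹¹]. U has variance 64 for the period baseline and 64 + 2s² for Visit 3.

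- Period baseline: 3.20%; × 54 = 1.7 patients.
- Visit 3 in Periods 2 and 3: 3.79%, 6.90%, 15.27%. Pooled with Period 1: 3.60%, 5.67%, 11.25%; × 54 = 1.9, 3.1, 6.1 patients.

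**Precision of a QTcF treatment difference.** Assumptions: 54 completers, patient SD 10 to 20 ms, the SAP's random-patient model fitted by REML to simulated trials.

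- Period change, Visit 3 covariate: mean SE 2.13 to 2.14 ms. Ignoring the covariate gives √(2 × 128/54) = 2.18, so it contributes almost nothing.
- Period change, period covariate: 1.72 to 2.04 ms.
- Visit 3 change and covariate: 1.58 to 2.46 ms; algebra √(2(64 + s²)/54) = 1.59, 1.82, 2.46.

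The ratio of the first to the second runs from 1.05 (2.14/2.04) to 1.24 (2.13/1.72).

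A separate derivation removes patient effects completely and takes ρ as the within-period correlation of pre- and post-dose residuals. The ratio is then √[4(1 − ρ)/(2(1 − ρ²))] = √[2/(1 + ρ)] = 1.41, 1.26, 1.15, 1.07 for ρ = 0, 0.25, 0.5, 0.75. It is larger because that analysis uses the within-patient slope alone. The SAP model uses one slope for between- and within-patient variation.

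**Sensitivity to the 8 ms.** With a within-period SD of 5 or 12 ms, the any-time count per 54 patients under the period baseline is about 0 or 11.5. With Visit 3 it is 0.0 to 2.7, or 11.7 to 14.2. The SE ratio is 1.02 to 1.12 at 5 ms and 1.10 to 1.31 at 12 ms.

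**The case against.** Section 6 already declares the direction of the change, so most of the correction carries out an announced decision. The mismatch in the model arises only if Section 6 governs; under 3.1 the model is coherent. Even the mixed pairing gives an unbiased treatment contrast under randomisation, in safety analyses of a study the SAP calls exploratory. These points are right, and they limit the matter to clarity and precision. They do not remove the conflict, because under either reading one section is wrong.

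The sizes rest on an assumed within-period SD, and the absolute flag counts move widely with it. That also stands, and the range is shown. The counts use 54 completers, whereas the safety set includes everyone dosed with a treatment, so actual counts would be somewhat higher.

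Some supporting text is weaker than it looks. SAP 3.1.2 is a general rule, and some other variables do have period baselines. Table 4 need not repeat a definition given once elsewhere, provided that definition is unambiguous. The protocol's withdrawal criteria also use period pre-dose values ("increase of >40 mmHg from pre-dose at Day 1 of each treatment period" for systolic pressure, ">60 ms change from pre-dose at Day 1 of each treatment period" for QTcF). They operate in real time and need not share the tabulation baseline. They show only that a Visit 3 baseline would tabulate different increases from those the criteria count. Whether the Visit 3 covariate was left over or intended cannot be known from the documents.

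**Conclusion.** The concern holds. SAP 3.1 and Section 6 give incompatible current definitions, and the covariate in 4.4.1.3 fits only the one that Section 6 says was replaced.

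The conflict should be corrected, but it does not threaten the trial's main conclusions. The extra flags under a Visit 3 baseline fall about equally on all treatments. The covariate mismatch costs roughly 5% to 24% in confidence interval width at the assumed 8 ms, and 2% to 31% over 5 to 12 ms. All these sizes rest on assumed variances.

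A Visit 3 baseline used throughout would also be coherent, and it could be more or less precise than the period baseline depending on between-period variation. What cannot stand is having both.

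**What to change.** Before unblinding:

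1. In SAP 3.1, define baseline for vital signs, laboratory (including i-STAT) and ECG variables as the last assessment before the first dose of IP in each period, as Section 6 announces.
2. In SAP 4.4.1.3, make the heart rate and QTcF covariate the pre-dose value of the same period instead of the Visit 3 value.
3. State that Tables 4, 5 and 6 and the laboratory shift tables built on the Table 3 limits use this baseline.

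Adding each patient's mean baseline as a second covariate is optional; it would separate the within-patient from the between-patient slope.

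The cost is SAP wording and the matching program line. Pre-dose ECG, blood pressure, i-STAT and laboratory values are already scheduled at Visits 3, 6 and 9. No outcome data are needed to make the change, and no efficacy analysis or withdrawal criterion is altered.

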3.1.1 Handling of missing or partial dates

For date of COPD diagnosis, partial dates will be imputed as follows.

- For dates with missing day and month (year is present), January 1 will be assigned to the missing fields.
- For dates with missing day only (month and year are present), the first day of the month will be assigned to the missing day.

For date of most recent COPD exacerbation, partial dates will be imputed as follows.

- For dates with missing day and month (year is present), December 31 will be assigned to the missing fields provided it does not result in a date post screening visit, in which case last day of month preceding month of screening visit will be used.
- For dates with missing day only (month and year are present), the last day of the month will be assigned to the missing day.

3.1.1.1 Imputation for concomitant medication start and stop dates

For prior or concomitant medications, including relief medications, incomplete (ie, partial or completely missing) start dates and/or stop dates will be imputed.

When the start date and the stop date are both incomplete for a patient, impute the start date first.

Incomplete start date

The following rules will be applied to impute the missing numerical fields. In addition, if the stop date is complete and the imputed start date is after the stop date, then the start date will be imputed using the stop date. If the stop date is present and implies that the medication is concomitant (ie, stop date is on or after the date of first dose of IP in the study), but the start date is completely missing, then the start date of the medication will be imputed with the date of first dose of IP.

For start dates with missing day and month (year is present):

- If the year of the incomplete start date is the same as the year of the date of the first dose of IP in the study, then the day and month of the date of the first dose will be assigned to the missing fields.
- If the year of the incomplete start date is prior to the year of the date of the first dose of IP in the study, then December 31 will be assigned to the missing fields.
- If the year of the incomplete start date is after the year of the date of the first dose of IP in the study, then January 1 will be assigned to the missing fields.

For start dates with missing month only (day and year are present):

- The day will be treated as missing and both month and day will be replaced according to the above procedure.

For start dates with missing day only (month and year are present):

- If the month and year of the incomplete start date are the same as the month and year of the date of the first dose of IP, then the day of the date of the first dose of IP will be assigned to the missing day;
- If either the year of the incomplete start date is before the year of the date of the first dose of IP or if both years are the same but the month is before the month of the date of the first dose of IP, then the last day of the month will be assigned to the missing day;
- If either the year of the incomplete start date is after the year of the date of the first dose of IP or if both years are the same but the month is after the month of the date of the first dose of IP, then the first day of the month will be assigned to the missing day.

Incomplete stop date

The following rules will be applied to impute the missing numerical fields. If the stop date is completely missing, replace it with the last dose date. If the imputed stop date is before the start date (imputed or non-imputed start date), then the imputed stop date will be equal to the start date.

For stop dates with missing day and month (year is present):

- If the year of the incomplete stop date is the same as the year of the date of the last dose of IP, then the day and month of the date of the last dose will be assigned to the missing fields.
- If the year of the incomplete stop date is prior to the year of the date of the last dose of IP, then December 31 will be assigned to the missing fields.
- If the year of the incomplete stop date is after the year of the date of the last dose of IP, then January 1 will be assigned to the missing fields.

For stop dates with missing month only (day and year are present):

- The day will be treated as missing and both month and day will be replaced according to the above procedure.

For stop dates with missing day only (month and year are present):

- If the month and year of the incomplete stop date are the same as the month and year of the date of the last dose of IP, then the day of the date of the last dose will be assigned to the missing day.
- If either the year of the incomplete stop date is before the year of the date of the last dose of IP or if both years are the same but the month is before the month of the date of the last dose of IP, then the last day of the month will be assigned to the missing day.
- If either the year of the incomplete stop date is after the year of the date of the last dose of IP or if both years are the same but the month is after the month of the date of the last dose of IP, then the first day of the month will be assigned to the missing day.

Incomplete time in start or stop date

Note that when dates are recorded using time (from 00:00 until 23:59) and if time is missing in a start date record, time = 00:01 will be assigned; if time is missing in a stop date record, then time = 23:59 will be assigned.

